9.2. Sample Size Determination

Cope-Yokoyama et al (Cope-Yokoyama, 2010) reviewed 6 previous liver biopsy studies on patients with WD before and after treatment with various SoC medications. From this review, data from 37 patients were available to calculate a weighted average of Cu concentration after treatment of 570 $\mu\text{g Cu/g dry liver}$. In addition, 13 individual patient data were available for both before and after treatment, with a standard deviation of paired difference of 319. It is expected that 48 weeks of treatment with ALXN1840 will reduce Cu concentration by 40%, from 570 to 342, for a reduction of 228. Using a t-test statistic, 24 patients in ALXN1840 will provide 92% power at a one-sided significance level of 0.025 to detect a reduction of 228, with a standard deviation of paired difference of 319, in Cu concentration.

Approximately 28 patients will be enrolled to accommodate a 15% dropout rate, such that approximately 24 evaluable patients complete the study.

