7.2. Efficacy Analyses

All efficacy analyses and summaries will be based on the FA Set in the Treatment Period. Additionally, the primary analysis will be performed on the PP Set in the Treatment Period. A 2-sided Type I error rate of 0.05 will be used to define statistical significance for all endpoints

without adjusting for multiplicity. Sample SAS code for the following analyses can be found in Section 9.5.

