7.2.1. Primary Analysis

The primary objective of this study is to evaluate change from Baseline in liver Cu concentration following treatment with ALXN1840 at Week 48 in patients with WD. The primary analysis will be performed using the FA Set in the Treatment Period.

To assess the reduction in liver Cu concentration, liver biopsies will be taken during the Screening Period and at Week 48 of Treatment Period, where the assessment from Screening will be regarded as Baseline. The change from Baseline in liver Cu concentration will be evaluated using a paired sample t-test on Baseline and Week 48 assessment values.

Prior to the primary analysis, multiple imputation will be used to impute missing data at Week 48 due to any reason based on Baseline values. Missing values at Week 48 will be imputed 20 times via SAS PROC MI, using the MCMC method, including Baseline and Week 48 liver Cu assessment values. A paired sample t-test analysis will be applied for each of the 20 imputed datasets, and then 20 sets of analysis results will be combined afterward via SAS PROC MIANALYZE. The combined estimate of the treatment effect, standard error (SE), 95% CI, and p-value will be summarized.

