9.5. Additional Details on Statistical Methods

The reference SAS codes used for efficacy analyses are as follows:

Multiple Imputation

Step 1:

```
proc mi data=xxx nimpute=20 seed=54321 out=yyy;  
  mcmc impute=monotone;  
  var BASE W48;  
run;
```

Step 2:

```
proc ttest data=xxx;  
  by _imputation_;  
  paired BASE*W48;  
run;
```

Step 3:

```
proc mianalyze data=xxx;  
  by AVISIT;  
  modeleffects ESTIMATE;  
  stderr STDERR;  
run;
```

Paired sample t-test

```
proc ttest data=xxx;  
  paired BASE*W48;  
run;
```

Wilcoxon Signed-rank test

```
proc univariate data=xxx;  
  var CHG;  
run;
```

MMRM

```
proc mixed data=xxx method=reml;  
  class AVISITN USUBJID;  
  model CHG=AVISITN BASE / solution ddfm=kr cl;  
  repeated AVISITN / subject=USUBJID type=UN;  
  lsmeans AVISITN / cl;  
run;
```

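### The primary result is pooled in PROC MIANALYZE without EDF=, so the t reference distribution is lost: the 95% CI is about 5% too narrow and the two-sided type I error is about 6% instead of 5%.

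*SAP*

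**What the plan says.** SAP 7.2.1 imputes missing Week 48 liver copper 20 times, runs a paired t-test in each completed dataset, and states that the "20 sets of analysis results will be combined afterward via SAS PROC MIANALYZE". The pooled estimate, SE, 95% CI and p-value are the primary result. SAP 7.2.1.4 judges it at a two-sided level of 0.05.

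SAP 9.5 introduces its code with "The reference SAS codes used for efficacy analyses are as follows". Step 1 is "proc mi data=xxx nimpute=20 seed=54321 out=yyy" with "mcmc impute=monotone". Step 3 is "proc mianalyze data=xxx", followed by a BY statement, the estimate as model effect, and "stderr STDERR". The degrees of freedom of the Step 2 t-test are not carried into Step 3. Neither EDF= nor any other rule for complete-data or small-sample degrees of freedom appears in SAP 7.2.1, SAP 9.5 or Protocol 9.4.1.1.

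The design calculation in Protocol 9.2 does rest on a t reference: "Using a t-test statistic, 24 patients in ALXN1840 will provide 92% power at a one-sided significance level of 0.025".

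**The concern.** When EDF= is absent, MIANALYZE uses Rubin's large-sample degrees of freedom, which assume that each completed dataset would support a normal-theory test. Here each dataset supports only a paired t-test on about 28 patients, so the pooled degrees of freedom should not exceed about 27. Under the large-sample formula, they grow without limit as the missing fraction falls. A trial with good follow-up therefore gets the least suitable reference distribution.

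The CI and p-value at stake are the primary ones, and both err in the anti-conservative direction. The SAP is also uneven on this point. It specifies Kenward-Roger degrees of freedom for the CGI-S model (SAP 7.2.2), a secondary endpoint, but has no small-sample rule for the primary endpoint. The baseline-carried-forward and observed-data sensitivity analyses (SAP 7.2.1.5) need no pooling and would use n − 1 degrees of freedom. They would then differ from the primary result partly through the reference distribution alone.

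**Working it through.** **Inputs.** Reduction 228, SD of paired difference 319, one-sided 0.025, 24 evaluable of about 28 enrolled, 15% dropout (Protocol 9.2, SAP 9.3); m = 20 imputations (SAP 7.2.1, 9.5); two-sided 0.05 (SAP 7.2.1.4). The FA Set requires an evaluable baseline copper value (SAP 6.2.2), so only Week 48 can be missing. The documents give no baseline–Week 48 correlation; a range of 0 to 0.8 is assumed.

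**The plan's own figure.** Noncentrality = (228/319) × √24 = 3.50. Noncentral t with 23 df gives power 91.8%, which matches the stated 92%. A pure normal approximation gives 93.8%. The sample size was therefore built on the t distribution.

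**Formulas.** Let r = (1 + 1/m)B/W, with B the between- and W the within-imputation variance.
- Default: df = (m − 1)(1 + 1/r)², infinite when B = 0.
- With EDF= ν (Barnard–Rubin): 1/df = 1/[(m − 1)(1 + 1/r)²] + 1/ν_obs, where ν_obs = [(ν + 1)/(ν + 3)] × ν × (1 − λ) and λ = r/(1 + r).

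**No between-imputation variance (closed form).** The critical value is 1.960.
- n = 28: 2P(t27 > 1.960) = 6.04%, one-sided 3.02%. Width ratio 1.960/2.052 = 0.955.
- n = 24: 2P(t23 > 1.960) = 6.22%, one-sided 3.11%. Width ratio 1.960/2.069 = 0.947.

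**One worked case, 4 of 28 imputed, correlation 0.5.** The median default df is 1,329, so 1 + 1/r = √(1,329/19) = 8.36 and r = 0.136. Then λ = 0.136/1.136 = 0.120, and ν_obs = (28/30) × 27 × 0.880 = 22.2. The small-sample df is 1/(1/1,329 + 1/22.2) = 21.8. Critical values are 1.962 as coded and 2.075 with EDF=27, a ratio of 0.945.

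**Simulation under the null, n = 28, 4 missing, m = 20, proper normal-model imputation, 60,000 trials per row** (Monte Carlo SE about 0.1 percentage point):

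| Correlation | Median df as coded | Median df, EDF=27 | Median CI width ratio | Two-sided error as coded | With EDF=27 |
|---|---|---|---|---|---|
| 0 | 2,758 | 22.9 | 0.9477 | 5.8% | 4.6% |
| 0.3 | 1,714 | 22.3 | 0.9464 | 5.8% | 4.6% |
| 0.5 | 1,329 | 21.8 | 0.9455 | 5.9% | 4.7% |
| 0.8 | 967 | 21.2 | 0.9442 | 5.9% | 4.6% |

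In the direction of the alternative, the error as coded is 2.8% to 3.0% against the nominal 2.5%. With 2 missing, a separate run of 40,000 trials gave 5.70% as coded and 4.60% with EDF=27. With 6 to 8 missing, the median df as coded is still about 250 to 1,130. Over 0 to 8 missing, the interval is 4.5% to 6.7% too narrow.

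**The case against.** The strongest reply is that the code is only a template. SAP 7.2 describes it with "Sample SAS code for the following analyses can be found in". As printed it cannot run: Step 1 writes to one dataset name, Steps 2 and 3 read another, and no step creates the inputs to Step 3. A programmer could add EDF=. That is true, but nothing in the SAP requires it, and adding it after the data are seen would be an unplanned change to the primary p-value.

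The effect is also modest. At the design effect, using 1.960 in place of the t critical value moves the probability of significance from 91.8% to 93.3% with 24 patients and from 95.4% to 96.2% with 28. A verdict changes only if the pooled statistic lies between about 1.96 and 2.08. The planned completer t-test would show such a case, but it would not correct the primary result. This stands as a limit on the weight of the point.

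The repair is not exact either: with imputation it is slightly conservative (4.6% to 4.7%), and with nothing missing EDF=27 gives (28/30) × 27 = 25.2 df, not 27.

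The most useful objection concerns Step 1. Because baseline is always present in the FA Set, the missingness pattern is already monotone, and the option "mcmc impute=monotone" would leave Week 48 values unimputed. The 20 datasets would be identical and the test would run on about 24 completers, for which the complete-data df is 23. EDF=27 would then still give 25.2 df and an error of 5.1%. That is far better than 6.2%, but the value of EDF= depends on Step 1 working as SAP 7.2.1 intends.

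**Conclusion.** The pooling step is wrong as written. An analyst who follows SAP 9.5 obtains a primary CI and p-value on an essentially normal reference, not the t reference implied by the paired t-test and used for the 92% power. The two-sided error is 5.7% to 5.9% with 2 to 4 of 28 values imputed, and 6.0% to 6.2% when no imputation takes place. The interval is about 5% too narrow.

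The closed-form figures assume normally distributed differences. The simulated ones add a bivariate normal model, values missing completely at random and the assumed correlations; the conclusion does not change across that range. The ceiling of 27 assumes an FA Set of no more than 28, whereas the documents say approximately 28. The point should be corrected before the primary analysis. It does not threaten the design, and at the planned effect it would rarely change the outcome.

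**What to change.** In SAP 9.5 Step 3, write `proc mianalyze data=xxx edf=<n − 1>;`, with n the number of patients entering each completed-data t-test: the FA Set for the primary analysis (27 if n = 28) and the PP Set for the per-protocol run. In SAP 7.2.1, add a sentence that the pooled CI and p-value use Barnard–Rubin small-sample degrees of freedom with that complete-data value.

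At the same time, confirm that Step 1 actually imputes Week 48, for example by using full MCMC imputation or a monotone regression method. If it does not, n in the rule is the number of completers (EDF=23 for 24).

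The cost is one code option, one sentence and a check of Step 1. No data collection or design feature changes. The critical value rises from about 1.96 to between 2.06 and 2.08, so the interval widens by about 5% to 6%.
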